6.2.3 Reporting Instructions

- **Food and Drug Administration**

An IND safety report will be submitted for any adverse event that meets all three definitions: possibly related to the study drug, unexpected, and serious. If the adverse event does not meet one of the above definitions, it should not be submitted as an expedited IND safety report.

Any relevant additional information that pertains to a previously submitted IND safety report will be submitted to FDA as a Follow-up IND Safety Report without delay, as soon as the information is available (21 CFR 312.32(d)(2)).

Suggested Reporting Form:

US FDA MedWatch 3500A:
<http://www.fda.gov/Safety/MedWatch/HowToReport/DownloadForms/default.htm>

- **CTI BioPharma**

All serious adverse events (SAEs) must also be faxed to CTI BioPharma's local safety representative at [name] within 24 hours of study staff awareness. The report should include deidentified Oncore® SAE report along with MedWatch form. It may also be emailed to [contact].

All pacritinib-related non-serious adverse events (any grade) should be reported to CTI at the end of the study.

SAEs (regardless of attribution) should be reported to CTI within 24 hours after the lead investigator learns of the event.

Sponsor-Investigator shall report investigational drug product quality complaints to CTI within 24 hours after the lead investigator learns of the event, or if the event or reporting time frame occurs during a weekend or holiday, the quality complaints will be submitted to CTI the following business day. This includes any instances wherein the quality or performance of a CTI product (marketed or investigational) does not meet expectations (e.g., color, odor, appearance, quality, safety, effectiveness, suspected contamination) or that the product did not meet the specifications defined in the application for the product (e.g., unexpected labeling or contents). The product quality also includes quality of the drug delivery device (in this case, the capsule). As such, device defects should be reported according to the instructions on the PQC Form provided by CTI.

6.3 Unanticipated Problem Involving Risk to Subject or Other (UPIRSO)

The investigator and his or her team will follow the Medical College of Wisconsin policies related to unanticipated problems involving risks to subjects or others. This information may be found on the [Human Research Protection Program website](#).

6.4 Subject Complaints

If a complaint is received by anyone on the study staff, it will be discussed with the study staff and will be addressed on a case-by-case basis. The PI will be notified of any complaints. Complaints will be reported to the IRB if indicated.

If the subject has questions about his or her rights as a study subject, wants to report any problems or complaints, obtain information about the study, or offer input, the subject can call the Medical College of Wisconsin/Froedtert Hospital research subject advocate at [contact]. This information is provided to the subject in their consent.

6.5 Product Complaint

A product complaint is a verbal, written, or electronic expression that implies dissatisfaction regarding the identity, strength, purity, quality, or stability of a drug product. Individuals who identify a potential product complaint situation should immediately contact the Drug Manufacturer and report the event. Whenever possible, the associated product should be maintained in accordance with the label instructions pending further guidance from a Drug Manufacturer representative. Product complaints in and of themselves are not Reportable Events. If a product complaint results in an SAE, an SAE form should be completed. All product complaints must be reported to CTI within 24 hours of study staff awareness at [contact]

7 PHARMACEUTICAL INFORMATION

7.1 Product Description

Pacritinib for oral administration is supplied in capsules containing 100 mg (as the free base) in red cap/gray body size 0 opaque hard gelatin capsules. The inactive ingredients are microcrystalline cellulose, magnesium stearate, and polyethylene glycol 8000. Each capsule contains 146 mg of pacritinib citrate, which is equivalent to 100-mg pacritinib free base.

Pacritinib capsules should not be opened or crushed. Direct contact of the powder in pacritinib capsules with the skin or mucous membranes should be avoided. If such contact occurs, affected areas should be washed thoroughly with water.

7.2 Mechanism of Action

Pacritinib is a macrocyclic Janus kinase inhibitor that is being developed for the treatment of myelofibrosis. It mainly inhibits Janus kinase 2 (JAK2) and Fms-like tyrosine kinase 3 (FLT3).

7.3 Product Supply

Pacritinib will be supplied in 100-mg capsules by CTI BioPharma.

7.4 Storage Conditions

The drug product should be stored in the pharmacy, hospital, clinic, or warehouse at controlled room temperature, 20°C to 25°C (68°F to 77°F), with excursions between 15°C and 30°C (59°F and 86°F) allowed. Patients should be instructed that storage temperatures for pacritinib in the home should be below 30°C (86°F).

7.5 Handling and Drug Accountability

The investigator is fully responsible for the investigational products at the trial site. Dispensing of investigational products will be delegated to delegated site staff. The person responsible for dispensing the investigational products will be responsible for maintaining adequate control of the investigational products and for documenting all transactions with them.

The investigator, or a responsible party designated by the investigator, will maintain a careful record of the inventory and disposition of all agents. Each participating site investigator, or authorized designee, is responsible for maintaining a careful record of inventory and disposition of all investigational agents received at the site. Use of the NCI Drug Accountability Record Form is recommended, but sites may use their own accountability logs per institutional standards. Sites

must ensure accountability records capture the same information as the NCI Drug Accountability Record Form and in addition, capture the preparation time. Any used or partially used vials may be destroyed on-site per the institutional standard of practice. Expired vials remaining at the end of the study may be destroyed onsite per institutional standards.

At every study visit, patients will return bottles in which pacritinib is supplied with all remaining untaken pacritinib capsules, if any. Patient compliance will be evaluated by pill count and through pill diary provided at each visit. (Appendix 10)

Patients on the study will maintain a “Subject Diary” to record the number of tablets/pills/capsules of study medications they take daily. On this diary, they will also record any side effects related to the study medications.

7.6 Contraindications

Supportive care therapies, except when prohibited by any of the below provisions, are permitted, including the use of low-dose aspirin. Corticosteroids (up to 20 mg/day of prednisone or equivalent) and/or hydroxyurea may be used for up to two weeks during the first month of treatment with pacritinib.

The following therapies and procedures are prohibited throughout the study:

- Antiplatelet or anticoagulation agents, with the exception of \leq 100 mg/day of aspirin.
- Growth factor therapies, including erythropoietin and thrombopoietin.
- Strong CYP3A4 inhibitors and strong CYP450 inducers, except as needed to treat AEs, with study PI approval.
- Any drugs with significant potential for QTc prolongation (Appendix 6), except as needed to treat AEs, with medical monitor approval.
- Splenic irradiation or splenectomy.

Ongoing Hemorrhage: Patients with active bleeding should not begin or continue treatment with pacritinib. Reports of serious bleeding events, including life-threatening and fatal events, have been reported in association with pacritinib use. Pacritinib should be discontinued before planned surgery.

Hypersensitivity: Patients with a known hypersensitivity to the active ingredient or any of the excipients of the drug product should not take pacritinib.

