5.3 Concomitant and Excluded Therapies

Patients should receive full supportive care, including transfusions of blood and blood products, antidiarrheal and antiemetic agents, and antibiotics when appropriate.

Patients may not receive other investigational agents during the study.

Patients must not receive treatment with any potent CYP3A4 inhibitors for one week prior to the administration of pacritinib and during treatment with pacritinib.

The following therapies and procedures are prohibited for all patients during the washout period and throughout the treatment phase of the study.:

- Strong CYP3A4 inhibitors (Appendix 3) and strong CYP450 inducers (Appendix 4), except as needed to treat AEs, with Medical Monitor approval.
- Any drugs with significant potential for QTc prolongation (Appendix 6), except as needed to treat AEs, with PI approval.

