7.7 Known Adverse Events

Based on the adverse effects observed in nonclinical toxicity studies, as well as data from clinical studies in patients with advanced MF, AML, and lymphoma, the investigator is advised to observe the following precautions:

Gastrointestinal: Diarrhea has been reported during treatment with pacritinib and generally occurs within the first eight weeks of treatment. Pacritinib-related diarrhea is usually low grade, with severe diarrhea (grade 3 or 4) occurring in 5.8% of patients. Early identification and intervention are critical for the optimal management of diarrhea. Antidiarrheal medications should be given to patients starting on pacritinib, with instructions to start taking to control symptoms at the first sign of diarrhea. Pre-existing diarrhea should be adequately controlled before beginning

therapy. Nausea, vomiting, and abdominal pain have also been reported in relation to pacritinib administration. Most cases were reported to be of low severity, and symptoms improved with supportive management without requiring discontinuation of treatment. Patients with significant GI symptoms despite optimal supportive care may have pacritinib interrupted or have the dose of pacritinib reduced per protocol.

Platelet Count Reduction: Clinically relevant decreases in platelet count have been observed in patients treated with pacritinib. Prior to initiating treatment, patients should undergo laboratory testing to establish their baseline hematology profile, including complete blood count with a white blood cell count differential, platelet count, and coagulation testing, including prothrombin, international normalized ratio, partial thromboplastin time, and thrombin time. While on pacritinib, patients should be monitored as specified in the protocol for severe thrombocytopenia. For clinically significant decreases in platelet count, the dose of pacritinib should be reduced or interrupted in accordance with protocol guidelines.

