9.2 Study Team

The study team minimally consists of the principal investigator, the clinical research coordinator, regulatory specialist, and the study biostatistician. While subjects are on study, the principal investigator will meet regularly with the research coordinator and the study biostatistician to review study status. This review will include but not be limited to reportable SAEs and UPIRSOs and an update of the ongoing study summary that describes study progress in terms of the study schema. The appropriateness of further subject enrollment and the specific intervention for the next subject enrollment is addressed. All meetings including attendance are documented.

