Antidepressant	SNRI: Venlafaxine (Effexor, Efexor) SSRI: Citalopram (Celexa, Cipramil); Escitalopram (Cipralex, Lexapro, Nexito, Anxiset-E [India], Exodus [Brazil], Esto [Israel], Seroplex, Elicea, Lexamil, Lexam, Entact [Greece], Losita [Bangladesh], Reposil [Chile], Animaxen [Colombia], Esitalo [Australia], Lexamil [South Africa]) Tetracyclic: Mirtazapine (Remeron) Tricyclic: Clomipramine (Anafranil); Desipramine (Pertofrane, Norpramine); Imipramine (melipramine) (Tofranil); Nortriptyline (Pamelor, Sensoval, Aventyl, Norpress, Allegron, Noritren, Nortrilen); Trimipramine (Surmontil, Rhotrimine, Stangyl)
Antiemetic	Dolasetron (Anzemet); Granisetron (Kytril, Sancuso, Gransol); Ondansetron (Zofran, Anset, Ondemet, Zuplenz, Emetron, Ondavell, Emeset, Ondisolv, Setronax); Palonosetron (Aloxi); Tropisetron (Only on Non US Market) (Navoban, Setrovel)
Antifungal	Fluconazole (Diflucan, Trican); Pentamidine (Pentam)
Antihistamine	Astemizole (Removed from Market) (Hismanal); Terfenadine (Removed from Market) (Seldane)
Antihypertensive	Isradipine (Dynacirc); Ketanserin (Only on Non US Market) (Sufrexal); Moexipril/HCTZ (Uniretic, Univasc); Nicardipine (Cardene)
Antilipemic	Probucol (Removed from Market) (Lorelco)
Antimalarial	Artemimol+piperaquine (Only on Non-US Market) (Eurartesim); Chloroquine (Aralen); Halofantrine (Only on Non-US Market) (Halfan); Primaquine phosphate
Antimania	Lithium (Eskalith, Lithobid)
Antimycobacterial	Clofazimine (Only on Non-US Market) (Lamprene)
Antinausea	Domperidone (Only on Non-US Market) (Motilium, Motillium, Motinorm Costi, Nomit)
Antineoplastic agent	Inotuzumab ozogamicin (Besponsa); Oxaliplatin (Eloxatin)
Antipsychotic	Cyamemazine (cyamepromazine) (Only on Non-US Market) (Tercian); Haloperidol (Haldol [US & UK], Alopoperidol, Bioperidolo, Brotopon, Dozic, Duraperidol [Germany], Einalon S, Eukystol, Halosten, Keselan, Linton, Peluces, Serenace, Serenase, Sigaperidol); Levomepromazine (methotriptazine) (Only on Non-US Market) (Nosinan, Nozinan, Levoprome); Levosulpiride (Only on Non-US Market) (Lesuride, Levazeo, Enliva [with rabeprazole]; Mesoridazine (Removed from Market) (Serentil); Perphenazine (Trilafon, Etrafon/Triavil, Decantan); Pimozide (Orap); Pipamperone (Only on Non-US Market) (Dipiperon [E.U], Propitan [Japan], Dipiperal, Piperonil, Piperonyl); Prothipendyl (Only on Non-US Market) (Dominal, Largophren, Timoval, Timovan, Tumovan); Thioridazine (Mellaril, Novoridazine, Thioril); Benperidol (Only on Non-US Market)

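### Sections 5.3 and 7.6 reverse who approves CYP and QTc-drug exceptions, and 5.4 denies any dietary restriction although Appendix 3 lists four foods; daily NSAIDs could also be added to the on-treatment list

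*Combined protocol and SAP*

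**What the plan says.** **Approvers.** Sections 5.3 (Concomitant and Excluded Therapies) and 7.6 (Contraindications) each list prohibited drugs, and each allows exceptions to treat adverse events:

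- 5.3, CYP drugs: "Strong CYP3A4 inhibitors (Appendix 3) and strong CYP450 inducers (Appendix 4), except as needed to treat AEs, with Medical Monitor approval".
- 5.3, QTc drugs: "Any drugs with significant potential for QTc prolongation (Appendix 6), except as needed to treat AEs, with PI approval".
- 7.6, CYP drugs: "Strong CYP3A4 inhibitors and strong CYP450 inducers, except as needed to treat AEs, with study PI approval".
- 7.6, QTc drugs: "Any drugs with significant potential for QTc prolongation (Appendix 6), except as needed to treat AEs, with medical monitor approval".

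The 5.3 list covers the washout period and the treatment phase.

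**Diet.** Section 5.4 says there are no dietary restrictions. Section 5.1.2 lets the capsules be taken regardless of meals. Appendix 3, the list of strong CYP3A4 inhibitors to which 5.3 points, includes grapefruit, grapefruit juice, Seville oranges and star fruit.

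**Bleeding risk.** Exclusion 15 (Section 4.5, Eligibility Confirmation) bars several drug groups that raise bleeding risk in the 14 days before Day 1: anticoagulants, antiplatelet agents (aspirin up to 100 mg/day excepted), anti-VEGF agents and daily COX-1 inhibiting NSAIDs. On treatment, 7.6 bars antiplatelet and anticoagulation agents with the same aspirin allowance. Section 5.3 has no bleeding-risk item.

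**The concern.** A treating clinician who needs an exception gets a different answer depending on which section is open. This can arise in routine management of side effects. Section 5.3 says supportive care should include "antidiarrheal and antiemetic agents, and antibiotics when appropriate". Section 7.7 records that "Nausea, vomiting, and abdominal pain have also been reported in relation to pacritinib administration"; in the myelofibrosis studies summarised in 1.5.4, nausea was reported in 37% and vomiting in 24% of treated patients. The antiemetic row of Appendix 6 names, among others, "Granisetron (Kytril, Sancuso, Gransol); Ondansetron (Zofran, Anset, Ondemet". For ondansetron, 5.3 says to ask the PI and 7.6 says to ask the medical monitor. QTc prolongation is itself a listed effect of pacritinib, so this approval is a real safeguard.

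Staff advising a patient on diet would naturally open 5.4, and would there miss the foods in Appendix 3.

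On NSAIDs, a man who could not enter because of daily use in the fortnight before Day 1 could, on the current wording, begin daily use once treated. Section 7.7 reports serious bleeding with this drug, including life-threatening and fatal events.

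**Working it through.** The plan gives no figure on this point, so the check is a side-by-side reading plus counts from the appendices.

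**Step 1: approvers.**

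| Exception | 5.3 | 7.6 |
|---|---|---|
| CYP3A4 inhibitors, CYP450 inducers | Medical Monitor | PI |
| QTc-prolonging drugs | PI | Medical monitor |

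Both of the two assignments are reversed. No other section states an order of precedence. The nearest relevant text is exclusion 16, which at entry leaves a shorter QT-drug washout to the PI.

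**Step 2: drugs on more than one list.** Appendix 3 has 26 entries and Appendix 4 has 10, so 36 in all.

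- Appendix 3 entries also in Appendix 6: ciprofloxacin, clarithromycin, erythromycin, fluconazole, norfloxacin, quinidine, saquinavir and telithromycin (8), plus lopinavir and ritonavir, which Appendix 6 lists as a combination (2). 8 + 2 = 10 of 26.
- Appendix 4 entries also in Appendix 6: efavirenz, 1 of 10.
- Total: 10 + 1 = 11 of 36.

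For these 11, each section names both roles, one on the CYP ground and one on the QTc ground. Neither says whether both approvals are needed or one is enough. For the other 36 − 11 = 25 entries (4 of them foods, so 21 drugs), and for drugs that are only in Appendix 6, the two sections name different approvers outright.

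**Step 3: how much of Appendix 6 bears on supportive care.** The antiemetic row names 5 drugs; leaving out tropisetron, marked non-US, 4 remain. The antibiotic row names 17; leaving out 4 marked as removed from the market and 2 marked non-US, 17 − 4 − 2 = 11 remain.

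**Step 4: foods.** 4 of the 26 Appendix 3 entries are foods, counting grapefruit and grapefruit juice separately as the appendix does. The food-effect statement in 5.1.2 concerns meals. It fits the answer in 5.4 but does not deal with these four items.

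**Step 5: NSAIDs.** Daily COX-1 NSAIDs appear in 0 of the 2 on-treatment lists. They cannot safely be read into the antiplatelet item of 7.6, because exclusion 15 lists the two groups separately. The opening of 7.6 permits supportive care unless one of its provisions prohibits it, so an unlisted NSAID used as supportive care is allowed. The other provisions record use (Study Calendar), give a general caution about drugs affecting hemostasis (7.7), or act once bleeding has occurred (Table 1 in 5.2.2, and the bar on treating patients with active bleeding in 7.6). None bars daily use.

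**The case against.** **Approvers.** Under either section the drug stays barred until someone approves it, so the likely harm is delay or approval by the wrong person, not unrestricted use. Appendix 6 bars named drugs, not whole classes. Section 7.7 calls most nausea, vomiting and abdominal pain low in severity, and the documents give no rate of use. All of this stands and limits the size of the point. It does not remove the reversal.

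A reader might go further and infer that no Medical Monitor exists, so that no complete approval could ever be given. The supplied text mentions the role only in 5.3 and 7.6, and 9.2 says "The study team minimally consists of the principal investigator, the clinical research coordinator, regulatory specialist, and the study biostatistician". The documents do not support that inference: 9.2 sets a minimum team, which leaves room for other roles, and contact and signature pages were removed from the text under review.

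**Foods.** Section 5.3 speaks of therapies and procedures, exclusion 8 of systemic treatment, and the CYP item in 7.6 does not cite Appendix 3. Fruit is not naturally a therapy, so the ban reaches the foods only through the appendix. That is fair. But Appendix 3 lists them without exempting them. If they are meant to be avoided, 5.4 is wrong; if not, the list misleads. Either way the text needs correcting.

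**NSAIDs.** It is tempting to call the omission an error too. It is not a contradiction: exclusion 15 is an entry rule, 7.6 is an on-treatment list, and anti-VEGF agents are likewise not carried over. Other protections also apply here. The trial requires a platelet minimum of 100,000 (unit printed as per mL), limits PT/INR and PTT, excludes recent grade 2 or higher bleeding unless an inciting event caused it, repeats blood counts and holds drug around invasive procedures. The myelofibrosis trials had no platelet-count exclusion, and PERSIST-2 enrolled patients at or below 100,000/µL, so their bleeding experience may not transfer directly. This objection stands, and the NSAID change is therefore offered only as an improvement.

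**Conclusion.** Two points are wrong as written, both minor. The approver is reversed for 2 of 2 exceptions. Section 5.4 conflicts with an appendix in which 4 of 26 entries are foods, on the reading that 5.3 adopts the Appendix 3 list as it stands. The third point, daily COX-1 NSAIDs missing from both on-treatment lists, is a safety gap that is cheap to close, not a contradiction.

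The ground is patient safety and consistent conduct. Nothing here changes the primary endpoint, the one-sided 10% level, the 80% power or the 46 subjects. The documents give neither the frequency of use of these drugs and foods nor the size of any interaction, so the number of men affected cannot be estimated.

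**What to change.** 1. **Approvers (5.3 and 7.6).** Name one approver for each exception, identical in both sections. The PI is a natural choice, given the role in exclusion 16. State which approval covers a drug that is on both a CYP list and Appendix 6.
2. **Diet (5.4).** Say that meal timing is not restricted, but that grapefruit, grapefruit juice, Seville oranges and star fruit (Appendix 3) are to be avoided during the washout and treatment periods.
3. **Optional improvement (7.6).** Add daily COX-1 inhibiting NSAIDs beside the antiplatelet and anticoagulant ban, keeping aspirin up to 100 mg/day. Consider the anti-VEGF agents of exclusion 15 at the same time.

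The cost is amendment wording in 5.3, 5.4 and 7.6, with no added visits or patients. The one small downside, from item 3, is fewer analgesic options for men on study.

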7.7 Known Adverse Events

Based on the adverse effects observed in nonclinical toxicity studies, as well as data from clinical studies in patients with advanced MF, AML, and lymphoma, the investigator is advised to observe the following precautions:

Gastrointestinal: Diarrhea has been reported during treatment with pacritinib and generally occurs within the first eight weeks of treatment. Pacritinib-related diarrhea is usually low grade, with severe diarrhea (grade 3 or 4) occurring in 5.8% of patients. Early identification and intervention are critical for the optimal management of diarrhea. Antidiarrheal medications should be given to patients starting on pacritinib, with instructions to start taking to control symptoms at the first sign of diarrhea. Pre-existing diarrhea should be adequately controlled before beginning

therapy. Nausea, vomiting, and abdominal pain have also been reported in relation to pacritinib administration. Most cases were reported to be of low severity, and symptoms improved with supportive management without requiring discontinuation of treatment. Patients with significant GI symptoms despite optimal supportive care may have pacritinib interrupted or have the dose of pacritinib reduced per protocol.

Platelet Count Reduction: Clinically relevant decreases in platelet count have been observed in patients treated with pacritinib. Prior to initiating treatment, patients should undergo laboratory testing to establish their baseline hematology profile, including complete blood count with a white blood cell count differential, platelet count, and coagulation testing, including prothrombin, international normalized ratio, partial thromboplastin time, and thrombin time. While on pacritinib, patients should be monitored as specified in the protocol for severe thrombocytopenia. For clinically significant decreases in platelet count, the dose of pacritinib should be reduced or interrupted in accordance with protocol guidelines.

Bleeding: Pacritinib may increase the risk of bleeding. Reports of serious bleeding events, including life-threatening and fatal events, have been reported. These bleeding events were generally without lasting sequelae, although life-threatening and fatal events of hemorrhage, including intracranial hemorrhage, were observed more frequently in pacritinib-treated patients compared with BAT patients. Risk factors for bleeding with pacritinib may include prior bleeding events and anti-platelet and anti-coagulant medications in addition to severe thrombocytopenia. Concomitant use of drugs affecting hemostasis, such as aspirin and other antiplatelet agents, other anticoagulants, heparin, and thrombolytic agents, may increase the risk of bleeding. Refer to the protocol for guidance on dose modifications for pacritinib-related bleeding events.

Cardiac: QTc prolongation has been observed in patients treated with pacritinib. Prior to initiating treatment with pacritinib, patients should undergo an ECG to establish baseline QTc and an echocardiogram (or other appropriate methodology) to establish baseline left ventricular ejection fraction; patients should be monitored periodically for changes in their QTc. Pacritinib should not be used in patients with uncontrolled cardiac dysrhythmias, QTc prolongation >450 ms, or other factors that increase the risk for QT prolongation (e.g., heart failure, hypokalemia, hypomagnesemia, or a history of long QT interval syndrome). Caution should be used when co-administering other medicinal products with the potential to elongate QT interval. Ejection fraction should be monitored at baseline, after one month on treatment, after three and six months on treatment, and every six months thereafter; pacritinib dose should be modified if significantly reduced ejection fraction is detected. Additional ECG and ejection fraction assessments should be performed as clinically indicated. Refer to the protocol for guidance on dose modifications for pacritinib-related QTc prolongation.

General: Additional AEs commonly (>10% of patients) reported during pacritinib administration include fatigue, peripheral edema, pyrexia, decreased appetite, and pruritus. Adverse events and SAEs in the SOC of infections and infestations have been frequently reported, but none of these events were considered atypical for this population. Neoplasms, typically nonmelanoma skin cancers, have been reported in patients treated with pacritinib and were clustered in patients with geographic and other risk factors for skin malignancy, making further conclusions difficult. Participants in clinical studies of pacritinib will be monitored closely for these AEs.

